13.8.5 Laboratory Parameters

Summary statistics for laboratory parameters specified in [Section 9.2.4.5](#) will be presented by International System of Units overall. Shift-tables for hematology and biochemistry with respect to CTCAE v5 will be presented as well.

For urinalysis parameters, categories such as “positive” and “negative” will be used. The positive category could be further classified as positive “+” or borderline positive “(+)”.

For presentation of laboratory values as out of normal range, the flags are created using the normal ranges as provided by the central laboratory.

Box plots will be provided for hematology and biochemistry parameters showing the reference ranges for the parameters.

All laboratory data will be listed. In addition, all out of range laboratory data will be listed.

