Follow-up evaluations (FU 1, FU 2, FU 3) will be performed on 3 visits following contrast administration, at 24 ( $\pm$  4) hours, 48 ( $\pm$  4) hours, and 5 ( $\pm$  2) days post-dose, for safety assessments including clinical safety laboratory tests, measurement of blood manganese, ECG, vital signs, physical examination, including neurological assessments. Changes in concomitant therapies will be recorded. Follow-up evaluations at 24 ( $\pm$  4) hours and 48 ( $\pm$  4) hours can at the discretion of the investigator be performed as remote visits when required to ease the burden for the patient. Participants in the PK subgroup are required to have all assessments including blood samples as scheduled.

An additional follow-up visit (FU 4) for the optional brain MRI may be performed 7 (+ 2) days after mangoral-enhanced MRI of the liver only in those patients who underwent brain MRI due to any clinical reason within the last 6 months prior to mangoral-enhanced MRI and for whom previous brain MRI images are available for comparison (Section 6.2.4.1.2).

In a subgroup of patients, additional blood samples (6 mL per time point) will be drawn for the determination of pharmacokinetic parameters on the day of the liver MRI examination (day 0) at 0.25, 0.5, 1, 2, 3, 4, 6, 8, and 12 hours post-dose (Section 6.4). This PK subgroup will consist of 12 patients, including 4 patients currently on maintenance haemodialysis.

Each unenhanced and each mangoral-enhanced liver MRI examination will consist of axial T1- and T2-weighted image sequences and a diffusion-weighted imaging (DWI) sequence. Details of MRI acquisition parameters are described in Section [6.2.4.1.1](#).

Primary diagnostic efficacy in terms of visualisation of detected focal liver lesions will be evaluated centrally at an imaging core laboratory by 3 independent readers (Section [6.2.5](#)). Reading will be performed in 3 parts (Part I: unenhanced MRI alone; Part II: combined MRI, i.e. paired reading of both unenhanced and mangoral-enhanced images; Part III: mangoral-enhanced MRI alone). There will be a minimum 2-weeks gap between the reads to reduce recall bias. All independent central readers will be blinded to clinical data, site, and country information.

The site investigators will also evaluate unenhanced and mangoral-enhanced MRI images (on-site read). Their assessments will be used for the analysis of secondary variables.

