### 3.1 Discussion of study design

Mangoral is currently being developed for visualisation of focal liver lesions, including liver metastases, in patients where the use of GBCAs may be medically inadvisable or cannot be administered. Patients with severe renal impairment are at risk of experiencing serious adverse effects if they are given any of the intravenously administered contrast agents currently available on the market for liver MRI enhancement. NSF is a rare, but potentially fatal, complication of GBCAs that has been reported in patients with renal failure [\[21\]](#).

Previous clinical Phase I and II studies included healthy volunteers and patients with liver metastases. This Phase III study will be performed to assess the safety and diagnostic efficacy of mangoral in a patient cohort with severe renal impairment (eGFR < 30 mL/min/1.73 m^2, or increase in serum creatinine  $\geq$  0.3 mg/dL within 48 hours or  $\geq$  50% within 7 days) and who are being evaluated for known or suspected focal liver lesions. In addition, as patients with severe renal impairment are likely to need dialysis, patients on haemodialysis or peritoneal dialysis will be included in this study to obtain information on safety, pharmacokinetics, and diagnostic efficacy of mangoral in such patients.

A multicentre and multinational design is used to increase representativeness and to reduce bias.

Results of a previous clinical Phase II study demonstrated that signal intensity enhancement increased in liver parenchyma until 3 hours post-dose and there was no significant difference in the liver-to-lesion contrast between 3 and 6 hours after mangoral administration [\[16\]](#). Thus, the primary time point for mangoral-enhanced liver MRI chosen in this study is 4 hours after intake with a time window of  $\pm$  1 hour.

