9.2.4 Safety Parameters

This section defines the general principles for the analysis of categorical and continuous parameters, unless specified otherwise. In general, the analysis of all parameters will be done by visit/time point and treatment group and overall.

Categorical parameters will be descriptively summarized per visit/time point and overall post-baseline. For an overall post-baseline analysis, the worst value during the on-treatment period, including unscheduled visits, will be derived. If applicable, the number of not exact values will be displayed in the respective table. Continuous parameters will be descriptively summarized. Changes from baseline will be presented for all post-baseline visits/time points. Baseline values are defined as described in [Section 11.2.1](#).

Where applicable, continuous laboratory parameters will be classified as *low*, *normal*, or *high* based on reference (normal) ranges as provided by the central laboratories.

A listing of patients with values outside the reference ranges will be provided. All parameter values will be presented in a patient data listing including respective flagging with respect to reference ranges.

Unscheduled measurements of parameters will be presented in the patient data listing. In general, unscheduled measurements will not be included in the analysis.

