10.3 Analysis Populations

All patients enrolled in the study (fulfil all inclusion criteria, but none of the exclusion criteria and have been included in the clinical study at Visit 2) will be included in the safety analysis (safety population). The efficacy analysis will be performed in the full analysis set of patients (i.e. who have taken a single dose of the investigational medicinal product) and on a 'per protocol' basis, see definitions below ([Table 5](#)).

Table 5 Definition of analysis populations

Population	Description
Screened Patients	All patients with date of informed consent not missing.
Safety population (SAF) and enrolled patients	All patients enrolled in the study (fulfil all inclusion criteria, but none of the exclusion criteria and have been included in the clinical study at Visit 2).
Dosed Patients	All patients of the safety population who received the IMP.
Full analysis set (FAS)	All patients of the safety population who received the IMP and for whom the primary efficacy variable is assessable, i.e. all unenhanced / enhanced liver MRI images are assessable.
Per protocol set (PPS)	The 'per protocol' set defines the subset of the patients in the FAS without important protocol deviations that could affect the study objectives. All important protocol deviations will be manually reviewed by ICON and Ascelia to agree which to exclude from PPS.
PK population (PKS)	Defines the subset of patients in the FAS who have a blood sample taken at a PK timepoint (0.5, 1, 2, 3, 4, 6, 8 or 12 hours post-dose). These patients will be selected from a few sites that are able to include these patients and follow PK requirements.
Dialysis subgroup population (DSP)	All in the FAS currently on maintenance hemodialysis.
Brain MRI subgroup population (BMSP)	All patients in the FAS with brain MRI performed within 6 months prior to V3 who underwent the optional brain MRI 7 (+2) days after mangoral-enhanced MRI of the liver.

Demographic data and baseline characteristics will be displayed for the SAF, FAS and PPS populations. Efficacy data will be displayed for the FAS and the PPS populations. Safety data will be displayed for the SAF population. Manganese blood concentration data will be displayed for the FAS population, but PK parameters data will only be displayed for the PKS population.

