11.2 Definitions and Derived Variables

11.2.1 Definitions

For the statistical analysis, the different MRI methods will be denoted according to the following table.

Table 6 Labeling of MRI methods

MR1 Method	Short label (for tables etc.)
unenhanced MRI	UnMRI
mangoral-enhanced MRI	MeMRI
combined MRI (mangoral-enhanced MRI plus unenhanced MRI)	CMRI

In the following table, the definitions and calculation of derived variables are summarized.

Table 7 Further definitions

Variable / Term	Definition / Way of calculation
Baseline	The last assessment made before the administration of IMP will be used as baseline.

Variable / Term	Definition / Way of calculation
Change from baseline at visit	The difference between a value at time point and the value at baseline
Study day	
The day of IMP is defined as study Day 1.
 
Calculate the study day according to the following rules:
 
If date < date of IMP, then study day = date of IMP - Date.
 
If date ≥ date of IMP, then study day = Date – date of IMP + 1.

Age [years]	Year of informed consent – Year of birth
Age categories	
≥ 18 - < 65 years
 
≥ 65 - < 75 years
 
≥ 75 years

Body Mass Index (BMI)	$\text{BMI [kg/m}^2\text{]} = \frac{\text{Weight [kg]}}{\text{Height [m}^2\text{]}}$
Study duration [days]	Date of completion/discontinuation – date of informed consent + 1
Prior medication	
Any medication taken and stopped before the date of administration of mangoral.
 
If the end date of prior medication is missing or partial see Section 15.1.3.2.

Concomitant medication	
Any medication taken prior to the administration of mangoral and continuing after treatment or started after the date of administration of mangoral.
 
If the end date of concomitant medication is missing or partial see Section 15.1.3.2.

Adverse events	All untoward medical occurrences after signing the informed consent. These can be adverse events either prior to treatment or after treatment as collected in the CRF.
Time to onset of adverse events	Time to onset of adverse events will be calculated based on the administration start date time of IMP based on the imputed value for adverse event start date/time.

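### Renal and electrolyte laboratory summaries pool dialysis and non-dialysis patients, so session effects mix with any drug effect; presenting them by dialysis status is a cheap improvement

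*SAP*

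**What the plan says.** **Population.** Protocol 3.1 states that "patients on haemodialysis or peritoneal dialysis will be included in this study to obtain information on safety, pharmacokinetics, and diagnostic efficacy". The only planned number is in Protocol section 3: "This PK subgroup will consist of 12 patients, including 4 patients currently on maintenance haemodialysis". The rest of the trial has no target or cap for dialysis patients.

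**Sampling.** Protocol 6.3.5.2 and Table 8 include creatinine, urea, sodium, potassium, calcium, magnesium and chloride. Samples are taken within 24 hours before dosing, then at 2, 6, 24 and 48 hours and at 5 (±2) days. Neither that section nor the schedule in Table 9 relates sampling to dialysis sessions or asks for session times.

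**Analysis.**
- SAP 11.2.1: "The last assessment made before the administration of IMP will be used as baseline".
- SAP 9.2.4, for continuous safety parameters: "Changes from baseline will be presented for all post-baseline visits/time points".
- SAP 10.3: "Safety data will be displayed for the SAF population".
- SAP 13.8.5: laboratory summaries "will be presented by International System of Units overall", with CTCAE shift tables, box plots and listings, none by dialysis status.
- SAP 13.7.3: the subgroup analyses cover efficacy outputs only, and none is by dialysis.
- SAP 10.3, Table 5, defines a dialysis subgroup population as "All in the FAS currently on maintenance hemodialysis". No section of the SAP assigns an output to it.

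**The concern.** Dialysis removes creatinine and urea and shifts electrolytes directly. Baseline is simply the last pre-dose value, so in a dialysed patient the change from baseline depends on where the two samples fall relative to sessions. A session between them pushes the values the session clears downwards. A baseline drawn soon after a session makes the ordinary rise between sessions look like a post-dose deterioration. With no control arm, nothing else in the design separates this from an effect of the contrast agent.

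Two readings are at stake. One is the laboratory picture in patients not on dialysis, which the pooled mean dilutes. The other is the picture in dialysis patients, whom the protocol includes partly for safety information and whose changes cannot be read without knowing that they are dialysed and when.

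**Working it through.** **Document check.** The plan states no figure on this point, so there is none to reproduce. Setting the sections above side by side, dialysis status enters the SAP only through the subgroup population in Table 5, and that population feeds no laboratory output. Protocol 5.2 records concomitant therapy in a form that allows non-drug measures with start and end dates. Dialysis is not named there, and the SAP does not use such entries for laboratory data.

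**Illustration of size.** Let *f* be the share of patients on dialysis, *r* the true mean percentage rise in the others, and *d* the percentage fall in dialysis patients caused by a session. Then:

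pooled mean change = (1 − *f*) × *r* − *f* × *d*

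From the documents: 4 planned haemodialysis patients (Protocol section 3) and at least 80 patients (SAP 9.3), so 4/80 = 5% is a reference point. It is not an estimate of the actual share. Assumed, because the documents do not say: all other values of *f*, *r* = 10% or 20%, *d* = 30%, 50% or 70%, and a session between baseline and the sample in every dialysis patient.

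| Share *f* | r=10, d=50 | r=20, d=30 | r=20, d=50 | r=20, d=70 |
|---|---|---|---|---|
| 5% (4/80) | +7% | +17.5% | +16.5% | +15.5% |
| 10% | +4% | +15% | +13% | +11% |
| 20% | −2% | +10% | +6% | +2% |
| 30% | −8% | +5% | −1% | −7% |

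For example, at 5%: 0.95 × 10 − 0.05 × 50 = 9.5 − 2.5 = +7%.

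The pooled mean reaches zero at *f* = *r* / (*r* + *d*). For the four columns this gives 10/60 = 17%, 20/50 = 40%, 20/70 = 29% and 20/90 = 22%. Full masking thus needs a share of the order of 20 to 30% or more. The threshold is lower for a smaller rise and higher for a smaller session fall.

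**Same drug effect in both groups.** If dialysis patients also rise by 20% before a 50% removal, the pooled change is (1 − *f*) × 1.2 + *f* × 1.2 × 0.5 − 1. That is +17% at *f* = 5%, +8% at 20% and +2% at 30%.

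**Opposite direction.** Suppose there is no drug effect and baseline is drawn just after a session. An assumed 30% rise before the next session then gives a pooled change of *f* × 30%: +1.5% at 5% and +6% at 20%.

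**Within dialysis patients.** A 20% drug-related rise followed by a 50% removal appears as 1.2 × 0.5 − 1 = −40%. This does not depend on *f*.

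**By stratum.** The not-on-dialysis table shows the assumed 10% or 20% at every *f*.

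**The case against.** The case for leaving the plan alone has substance.

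- **The share may be small.** Only 4 dialysis patients are planned, and at 4/80 little is hidden. This stands, with the caveat that the 4 belong to the PK subgroup and the trial as a whole has no cap.
- **A session is unlikely before the early samples.** At 2 and 6 hours the patient is on site for dosing, MRI and ECG. This stands. The exposure is mainly at 24 hours, 48 hours and day 5.
- **Other statistics are more robust.** SAP section 10 also gives medians and quartiles. Take *r* = 10% and *d* = 50%, place all dialysis patients below the median, and assume normally distributed changes with an SD of 10 points in the others. The pooled median change is then +8.6%, +6.8% and +4.3% at shares of 10%, 20% and 30%. With an SD of 20 points it is +7.2%, +3.6% and −1.3%. This stands for patients not on dialysis.
- **Patient-level outputs do not cancel.** Shift tables count patients, so a fall in one cannot offset a rise in another. Listings show every value, clinically significant abnormalities become adverse events, and SAP 9.2.4 uses the worst post-baseline value for categorical parameters. This stands across patients. For a dialysed patient, though, the baseline grade and the worst grade both depend on session timing, and no listing is specified to show dialysis status.
- **Small groups.** SAP 7.1 drops some efficacy subgroups as too small to compare. The aim here is to separate a known source of variation, and no between-group comparison is needed.
- **The wording is innocent.** In a single-arm trial, an overall presentation simply means one column. The sentence itself is not the fault; the point is that no dialysis split appears elsewhere in the SAP. Layouts are in separate shells that cannot be seen here.

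A reader might also infer that renal safety is the trial's central safety question. The documents do not say so. Protocol 1.3 and 6.3.6 stress neurological and other organ toxicity, and severe renal impairment defines the population because gadolinium agents are restricted there.

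**Conclusion.** The point holds as a limit on interpretation. Pooled mean changes in creatinine, urea and electrolytes combine session effects with any drug effect, and a single-arm design cannot separate them afterwards.

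The effect on the pooled mean is small at about 5% on dialysis (+10% shows as +7%). It becomes serious at roughly 20 to 30% or more, under assumed session falls of 30 to 70% and a session in every dialysis patient before the sample. The actual share is not documented. For dialysis patients themselves, the change from baseline is confounded at any share.

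A reader might conclude that the tables will give false reassurance. The documents do not support that: the direction depends on when baseline falls relative to a session, and a false signal of harm is equally possible. Nor do they support saying that a deterioration in non-dialysed patients would go unseen, because the shift tables, listings and adverse event rules remain. The point does not touch the primary analysis or the type I error.

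**What to change.** In SAP 13.8.5, present creatinine, urea, sodium, potassium, calcium, magnesium and chloride by dialysis status in addition to overall. This covers the summary, change from baseline, shift table and box plot, on the safety population, with strata of any haemodialysis or peritoneal dialysis versus none.

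- Derive a dialysis flag for the whole safety population. The existing subgroup population cannot serve, because it omits peritoneal dialysis patients and anyone outside the full analysis set.
- Show dialysis status in the laboratory listings.
- Flag samples with a session between baseline and sampling wherever concomitant-therapy or source records give the dates, and state how many cannot be classified.
- State that drug-related renal and electrolyte changes will be read mainly from the not-on-dialysis stratum.

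The cost is a few more descriptive tables, small dialysis counts and a modest derivation for the wider flag. Dosing, the timing of dialysis and sampling, and the confirmatory analysis are unchanged.

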#### 6.3.5.2 Clinical safety laboratory tests

Blood samples for haematology and biochemistry tests as well as a urine sample for urinalysis for safety monitoring will be collected at baseline (within 24 hours prior to contrast administration), and 2 ( $\pm 0.5$ ) hours, 6 ( $\pm 1$ ) hours, 24 ( $\pm 4$ ) hours, 48 ( $\pm 4$ ) hours, and 5 ( $\pm 2$ ) days after administration of mangoral. A blood volume of approximately 12 mL will be drawn per time point. An overview of measured parameters is given in [Table 8](#).

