**Table 8 Clinical safety laboratory parameters (baseline and post-dose)**

Haematology: (central lab)	Haemoglobin Haematocrit Erythrocytes Leucocytes Thrombocytes Neutrophils Eosinophils, Basophils Lymphocytes Monocytes INR	Biochemistry: (central lab)	Alkaline phosphatase Aspartate aminotransferase (ASAT) Alanine aminotransferase (ALAT) Gamma-glutamyl transferase ( $\gamma$ -GT) Creatinine Glucose Urea Total Bilirubin Albumin Sodium Potassium Calcium Magnesium Chloride
Urinalysis: (local lab)	pH Leucocytes Blood Protein Glucose Urobilinogen Ketones Bilirubin Nitrite Specific density		

All blood tests (haematology, biochemistry) will be analysed at a central laboratory. Special tubes, labels, packaging, and sample handling instructions will be provided by the central laboratory. Blood sampling and handling procedures are described in the study-specific laboratory manual.

Urinalysis will be performed by using sites' standard of care dipsticks or using dipsticks provided by the central laboratory.

The investigator must document the clinical significance of abnormal laboratory values in the eCRF. If the clinically significant abnormal value is observed after administration of mangoral, the abnormality must also be recorded as an AE (Section 6.3.7). All clinically significant abnormal laboratory values observed at 5 ( $\pm$  2) days post-dose will be followed upon until they have normalised, or until there is no medical necessity for further blood tests in the investigator's opinion (Section 6.3.7.3).

After completion of all analyses, any leftover blood or blood samples will be destroyed immediately after the termination of the study.

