#### **8.1.6 Safety analyses**

AEs will be encoded using the MedDRA thesaurus in the most recent version available at the beginning of the study. This version will be used throughout the entire study. Updates of the MedDRA thesaurus will not be applied afterwards. The same will apply to the Anatomic Therapeutic Chemical Classification System developed by the World Health Organisation, which will be used for the coding of previous and concomitant medications. Frequency tables for coded previous and concomitant medication will be compiled

Frequency tables by system organ class and preferred term will be prepared based on patients experiencing an AE and based on the number of AEs. These frequency tables will also be prepared for AEs assessed as related to the investigational medicinal product. A frequency table will be created to give an overview of numbers of AE and patients with an AE in relation to investigational product, severity and seriousness (if an AE is recurring with the same term, the highest reported severity will be used for categorisation).

Results of vital sign measurements, physical examinations, neurological assessments, brain MRI assessment and ECG will be presented using descriptive statistics.

Laboratory data will be presented using descriptive statistics as well as using shift-tables with respect to normal ranges.

Concomitant diseases and medical history will be presented using frequency tables.

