2.0 Change History

Version / Date	Change Log
1.0 / 13-Nov-2020	Final (stable) version
1.1 / 15-Nov-2022	
Updated due to protocol v6 and v7 respectively as well as sponsor comments
 
Major changes:
 
 • Updated approvers section. • Updated based on CRF v5. • Updated changed from protocol section: definition of per protocol set and subgroup analyses planned. • Updated section on subgroup analyses. • Updated rules for handling of partial dates and times of medications and adverse events.
2.0 / 20-Dec-2022	
Revised to sponsor comments.
 
Major changes:
 
 • Additional ANOVA analyses on primary endpoint. • Removal of subgroup analyses by status of liver disease and additional subgroup analyses by sex instead. • Amended derivations for liver-to-lesion contrast and contrast to noise ratio. • Update to PK parameters to be derived. • Updated specification for intra-reader bland-altman plots.
3.0 / 14-Feb-2023	
Sample size estimation updated.
 
Missing reference added.

4.0/ 02-Jun-2023	
Minor editorial changes and corrections to align with shells.
 
Major changes
 
 • Removal of ANOVA analysis. • Laboratory shift tables is by CTCAE grade. • Concentration data listed and summarized for the safety analysis set instead of the full analysis set. • Clarification on patient management analysis. • Explanation on QTcB and QTcF re-derivations. • Updated wording of some analysis sets to be clearer.

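### SAP 13.8.5 drops the urinalysis shift table that Protocol 8.1.6 implies, without declaring it, and its named urine levels stop at +, so worsening above + would not show in the urinalysis summaries

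*SAP*

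**What the plan says.** Protocol 8.1.6 states: "Laboratory data will be presented using descriptive statistics as well as using shift-tables with respect to normal ranges". Protocol Table 8 lists urinalysis among the clinical safety laboratory parameters, beside haematology and biochemistry. Protocol 6.3.5.2 has urine collected on the same schedule as blood ("Blood samples for haematology and biochemistry tests as well as a urine sample for urinalysis for safety monitoring will be collected at baseline"), and then at 2, 6, 24 and 48 hours and at 5 days after dosing.

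SAP 13.8.5 says of shift tables: "Shift-tables for hematology and biochemistry with respect to CTCAE v5 will be presented as well". Its box plots cover the same two groups. For urine it says: "For urinalysis parameters, categories such as “positive” and “negative” will be used", followed by: "The positive category could be further classified as positive “+” or borderline positive", the borderline level being written (+).

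SAP 9.2.4 sets the general rule for categorical safety parameters: a summary per time point and one overall. For the latter: "For an overall post-baseline analysis, the worst value during the on-treatment period, including unscheduled visits, will be derived". Changes from baseline are mentioned directly after the sentence on continuous parameters.

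The SAP change history for version 4.0 records: "Laboratory shift tables is by CTCAE grade". Neither that entry nor SAP 7.1, which sets out changes from the protocol, mentions urinalysis. SAP 7.1 adds that the SAP prevails where the two documents conflict.

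**The concern.** Two matters meet here. The first is consistency: a laboratory group has lost a presentation that the protocol promised, and the section meant to record such changes is silent. Because the SAP prevails, the table will not be produced as the plan stands.

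The second is information. Everyone enrolled has chronic kidney disease with eGFR below 30 mL/min/1.73 m² or acute kidney injury. Protein or blood in the urine before dosing is plausible in such patients, and for them the relevant question is whether the finding gets worse. A summary that stops at + and is not paired with baseline cannot answer that. A steady percentage of positive results could be read as no urinary change while levels were rising within the positive category.

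**Working it through.** The plan states no figure on this point, so the check is a comparison of the passages followed by reasoning on what the planned summaries can show.

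**Protocol against SAP**

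- Scope of shift tables: laboratory data as a whole in Protocol 8.1.6; haematology and biochemistry only in SAP 13.8.5.
- Reference for the shift: normal ranges in the protocol; CTCAE version 5 in the SAP. The change history discloses this switch.
- Removal of urinalysis: disclosed neither in the change history nor in SAP 7.1. Protocol 8.1.11 expects deviations from the planned analysis to be defined in the SAP.

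**What the named urine levels can show**

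The documents do not state the dipstick scale. Protocol 6.3.5.2 allows different sticks: "Urinalysis will be performed by using sites' standard of care dipsticks or using dipsticks provided by the central laboratory". Assume for illustration that they read negative, (+), +, ++ and +++.

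- Negative to +: visible in the two-level and the three-level summary.
- (+) to +: not visible with two levels, because both are positive; visible if the optional split is used.
- + to +++: not visible with either, because + is the highest level the SAP names.

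**What follows from not pairing with baseline**

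Take two hypothetical patients. One is negative at baseline and positive at 24 hours; the other is positive and then negative. The per-visit summary gives 1/2 = 50% positive at both times. A shift table would show one patient worsening and one improving. The worst post-baseline value does not solve this, since a patient positive throughout and a patient newly positive fall in the same category.

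**Where worsening could still be seen**

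- Adverse event tables: Protocol 6.3.5.2 and SAP 9.2.4.5 require a clinically significant abnormal post-dose value to be recorded as an adverse event, and SAP 13.8.1 tabulates these by system organ class, preferred term and maximum grade. This depends on the investigator's judgement of each value.
- Listings: all laboratory data are listed. The out-of-range flags use central-laboratory ranges, whereas SAP Table 3 marks urinalysis as a local test, so the flags may not help with urine.
- pH and specific gravity: numeric measures, which would get change-from-baseline summaries if handled as continuous.
- Kidney function by another route: creatinine and urea are measured centrally at baseline and the same five post-dose times, and keep their shift tables and box plots.

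**Extent**

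Protocol Table 8 lists 10 urinalysis items. Without pH and specific gravity, 10 − 2 = 8 are affected, each read at baseline and five post-dose times.

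**The case against.** The strongest reply has four parts.

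First, the SAP wording is open. The categories are introduced as examples, the (+) split is allowed, SAP 15.1.4.2 displays every level of a categorical parameter, and SAP 10.0 lets ordinal ratings be treated as continuous. The table shells are a separate document and may contain more. This stands as a limit on certainty. But permission is not a plan, and no section commits to levels above + or to pairing with baseline for urine.

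Second, the protocol's own table would not have solved the problem. A shift table against normal ranges puts + and +++ together as abnormal. This is right, and it separates the two parts of the point: the undeclared omission is a departure from the protocol, while tabulating finer levels is an improvement beyond it.

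Third, the data may be coarse. If the case report form holds only negative, (+) and +, a finer table cannot be built. That is why the fix refers to the levels actually recorded.

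Fourth, renal safety does not rest on dipsticks, because creatinine and urea are fully tabulated. This also stands, and keeps the point small.

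A reader might go further and infer that worsening from a positive baseline can appear in no table at all, or that the listings and the investigator's judgement are the sole protection for renal safety. The documents support neither: clinically significant worsening reaches the adverse event tables, a move from (+) to + can change the counts if the split is used, and the biochemistry tables remain.

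**Conclusion.** The point holds as a minor one. SAP 13.8.5 narrows the shift tables of Protocol 8.1.6 to exclude urinalysis, and SAP 7.1 does not say so. Within the levels the SAP names, worsening beyond + would not show in the urinalysis summaries, and no comparison with the patient's own baseline is stated.

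The first conclusion rests on the text alone. The second assumes that dipsticks are read in ordered grades above +, that those grades are recorded, and that some patients are positive before dosing. The last is plausible in severe renal impairment, but the documents give neither a baseline rate nor a rate of worsening, so the number of patients affected cannot be estimated. Nor can the loss be expressed as statistical power, since SAP 13.8 plans descriptive summaries only and no test of urinalysis. The primary efficacy result is not touched.

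**What to change.** In SAP 13.8.5, state that dipstick parameters will be tabulated by the ordered levels actually recorded. Add a shift table of baseline level against the level at each post-dose time point and against the worst post-baseline level, with the number and percentage of patients who worsen and who improve by at least one level. Keep pH and specific gravity as numeric summaries. If the omission or a coarser cut is kept, declare and justify it in SAP 7.1.

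The change needs SAP wording and one table shell, repeated over up to 8 parameters and 5 + 1 = 6 comparisons with baseline. It needs no new procedures or patients, and no new data provided the levels were captured. Levels must be mapped across site and central-laboratory dipsticks, and a stick with fewer levels should use its own in order. Some cells will be sparse: with five levels (assumed) and the 80 patients of SAP 9.3, a full table has 5 × 5 = 25 cells and averages 80/25 = 3.2 patients per cell. The counts of worsening and improving patients will therefore be easier to read than the individual cells.
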